10.2.2.1 Overview of Adverse Events Rates per 100 Patient-Years of Study Drug Exposure

An overview of AEs per 100 patient-years of study exposure will be presented for upadacitinib 15 mg QD for the following AE categories.

- All TEAEs
- Treatment-emergent serious adverse events (SAEs)
- Treatment-emergent severe adverse events
- TEAEs reasonably possibly related to study drug
- TEAEs of special interest
- TEAEs leading to discontinuation of study drug
- TEAE leading to death

Additional AEs may be considered for tabulation/summary based on recommendations from Clinical and Safety as deemed appropriate.

10.2.2.2 Adverse Events Rates per 100 Patient-Years of Study Drug Exposure by SOC and PT

For upadacitinib 15 mg QD treatment group, the TEAE rate per 100 patient-years of exposure as outlined in Section 10.2.2 will be calculated overall, for each SOC and each PT, for each of the following events:

- All TEAEs
- Treatment-emergent serious adverse events (SAEs)
- Treatment-emergent severe adverse events
- TEAEs reasonably possibly related to study drug

- TEAEs leading to discontinuation of study drug
- TEAE leading to death

**10.2.2.3 Adverse Events of Special Interest Rates per
100 Patient-Years of Study Drug Exposure**

The Adverse Events of Special Interest (AESI) rate per 100 patient-years of exposure as outlined in Section 10.2.2 will be calculated overall, for each SOC and each PT, for each of the AESI listed in Section 10.2.1.6.

**10.2.2.4 Listing of Serious Adverse Events (Including Deaths) and
Adverse Events Leading to Study Drug Discontinuation**

All serious adverse events (SAEs), deaths, and adverse events leading to discontinuation of study drug will be listed.

10.3 Analysis of Laboratory Data**10.3.1 Variables and Units**

All laboratory parameters to be collected in this study are listed below. Laboratory parameters will be reported using the standard international (SI) units.

Table 12. List of Laboratory Variables

Laboratory Variables
Hematology
White Blood Cell (WBC) Count
Red Blood Cell (RBC) Count
Hemoglobin
Hematocrit
Platelets count
Neutrophils
Basophils
Eosinophils
Lymphocytes
Monocytes
Bands
Chemistry
Total Bilirubin
Alkaline Phosphatase (ALP)
Serum glutamic oxaloacetic transaminase (SGOT/AST)
Serum glutamic pyruvic transaminase (SGPT/ALT)
Total Protein
Albumin
Glucose
Triglycerides
Blood Urea Nitrogen (BUN)
Creatinine
Uric acid
Sodium
Potassium
Calcium
Inorganic Phosphorus
Creatine Phosphokinase (CPK)
Chloride

Table 12. List of Laboratory Variables (Continued)

Laboratory Variables
Chemistry (continued)
Bicarbonate
Cholesterol
LDL cholesterol
HDL cholesterol
International Normalized Ratio (INR) reflex only
Urinalysis
Specific Gravity
pH
Protein
Glucose
Ketones
Blood
Microscopic Examination (if needed)
Urobilinogen
Bilirubin
Leukocytes
Nitrites
Other
hs-CRP
QuantiFERON-TB Gold ^a
IgG and IgM
ESR

a. For annual follow-up, QFT is captured only for those with negative QFT at Screening.

10.3.2 Analysis of Laboratory Data for Period 1

The laboratory data will be summarized by the "as treated" treatment groups (upadacitinib 15 mg QD and the placebo group).

10.3.2.1 Assessment of Mean Change from Baseline and Percent Change from Baseline in Clinical Laboratory Variables

Analyses of mean change from baseline in continuous hematology, chemistry, and urinalysis variables which are measured longitudinally will be performed by visits and by "as treated" treatment group. For each change from baseline analysis, the following summary statistics will be presented for each treatment group: sample size, baseline mean, visit mean, and the mean, standard deviation, and median of the changes from baseline. An ANOVA model with treatment as a factor will be used to test statistical significance for the change from baseline mean among different treatment groups.

In addition, similar analyses will be conducted for percentage change from baseline in hemoglobin, LDL-C, HDL-C, triglycerides, total cholesterol (TC), TC/HDL and LDL/HDL.

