**Statistical Methods (Continued):****Safety:**

Safety analyses will be carried out using the Safety Analysis Set, which includes all subjects who receive at least one dose of study drug. Analyses will be conducted for Period 1 alone, as well as for Period 1 and Period 2 combined. Safety will be assessed by AEs, physical examination, laboratory assessments, ECG and vital signs. Frequency tables and lists of subjects with treatment-emergent AEs by preferred term as in the Medical Dictionary for Regulatory Activities dictionary, by system organ class, by severity, and by relationship to the study drug as assessed by the Investigator will be provided. The changes from baseline in vital signs, physical examination results, and clinical laboratory values will be analyzed in a descriptive manner. Shift of laboratory values from baseline to defined time points will be tabulated.

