#### **8.1.5.3 Analysis of Laboratory, Vital Sign, and ECG Data**

Changes from baseline by visit, and changes from baseline to minimum value, maximum value, and final values in continuous laboratory data, and vital signs will be summarized by treatment group.

Baseline values are defined as the last non-missing measurements recorded on or before the date of the first dose of study drug in Period 1.

The laboratory data will be categorized as Grade 1, Grade 2, Grade 3 and Grade 4 according to OMERACT criteria (Rheumatology Common Toxicity Criteria V.2.0). For creatine phosphokinase and serum creatinine, NCI CTC criteria will be used. The shift tables will tabulate the number and percentage of subjects with baseline and post-baseline values by grade level.

Listings will be provided for potentially clinically significant laboratory values and vital signs.

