4.3 Sample Size

The planned total sample size of 322 for this study provides over 90% power for a 21.7% difference in ACR20 response rate at Week 12 (assuming a placebo ACR20 response rate of 36.7%), at two-sided significance level of 0.05 and accounting for a 10% dropout rate. This sample size will also provide at least 90% power for most of the key secondary endpoints, including change from baseline in DAS28 (CRP), ACR50 response rate, LDA and CR based on DAS28 (CRP), and SF-36 PCS, at two-sided significance level of 0.05 and accounting for a 10% dropout rate.

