9.2.3 Key Secondary Efficacy Analyses

Ranked key secondary endpoints (at Week 12) are:

1. Change from baseline in DAS28 (CRP);
2. Change from baseline in HAQ-DI;
3. Change from baseline in Short Form-36 (SF-36) Physical Component Score (PCS);
4. Proportion of subjects achieving LDA based on DAS28 (CRP) ≤ 3.2 ;
5. Proportion of subjects achieving Clinical remission (CR) based on DAS28 (CRP);
6. Proportion of subjects achieving LDA based on CDAI ≤ 10 ;

Other key secondary endpoints (at Week 12) are:

1. ACR50 response rate;
2. ACR70 response rate;
3. ACR20 response rate at Week 1.

For binary endpoints, frequencies and percentages will be reported for each randomized treatment group. Similar analyses as for the primary endpoint will be conducted.

For the major RA continuous endpoints DAS28 and HAQ-DI change from baseline, statistical inference will be conducted using analysis of covariance (ANCOVA) coupled with MI for missing data handling. Specifically, the ANCOVA model will include treatment as the fixed factor, and the corresponding baseline value and the stratification factor country as the covariates. For other continuous endpoints, statistical inference will be conducted using the MMRM model as described in Section 9.1.2, with the main stratification factor being country. From both the MI and MMRM analyses, the LS mean and 95% CI will be reported for each randomized treatment group; the LS mean treatment difference and associated 95% CI and p-value will be reported comparing upadacitinib group with the placebo group.

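### Period 1 laboratory changes are tested by an ANOVA with treatment only; adding each parameter's baseline value as a covariate would give a more precise test that does not shift with chance baseline imbalance

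*SAP*

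**What the plan says.** For Period 1, SAP 10.3.2.1 tabulates, by visit and as-treated group, "sample size, baseline mean, visit mean, and the mean, standard deviation, and median of the changes from baseline". It then adds a test: "An ANOVA model with treatment as a factor will be used to test statistical significance for the change from baseline mean among different treatment groups". The same section states that "similar analyses will be conducted for percentage change from baseline in hemoglobin, LDL-C, HDL-C, triglycerides, total cholesterol (TC), TC/HDL and LDL/HDL". Neither baseline nor country appears in the model, there or elsewhere for laboratory data.

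The baseline needed for adjustment is already defined. Protocol 8.1.5.3 says: "Baseline values are defined as the last non-missing measurements recorded on or before the date of the first dose of study drug in Period 1".

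Two other places bear on the choice:

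- **Period 1 efficacy.** For DAS28 and HAQ-DI, SAP 9.2.3 says that "the ANCOVA model will include treatment as the fixed factor, and the corresponding baseline value and the stratification factor country as the covariates". The MMRM for the other continuous Period 1 endpoints (SAP 9.2.3, 9.2.4 and Appendix C) also carries baseline and country.
- **The protocol on laboratory data.** The safety paragraph of the synopsis says that "clinical laboratory values will be analyzed in a descriptive manner". Protocol 8.1.5.3 says only that changes will be summarized, and 8.1.5.1 that they will be analyzed. None of these announces a test.

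**The concern.** The baseline value is measured, defined and printed in the same table, yet the model that produces the p-value does not estimate how strongly the follow-up value depends on it. Two things follow. The treatment difference carries avoidable noise. And if the arms happen to differ at baseline, part of the apparent treatment difference is regression to the mean.

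The parameters involved matter for this drug. Protocol 6.1.1.3 lists lipid changes, anemia, neutropenia, lymphopenia, creatinine, transaminases and CPK among the adverse events of special interest. Lipids lean most on this analysis: SAP Table 11 has no lipid row, and the grading criteria behind the shift and Grade 3 or 4 tables contain no lipid item. Apart from reported adverse event terms, the mean and percent change comparison is the only Period 1 between-arm look at lipids. In a safety analysis, lost precision works against seeing harm.

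**Working it through.** **The plan's own figure.** The SAP gives no figure for the laboratory test. Its one power statement, in 4.3, is: "The planned total sample size of 322 for this study provides over 90% power for a 21.7% difference in ACR20 response rate". The placebo rate is taken there as 36.7%, so upadacitinib is 36.7% + 21.7% = 58.4%. With 10% dropout, 161 x 0.9 = 144.9 per arm, and two-sided alpha 0.05 gives 96.3% power. The stated figure reproduces; it does not bear on the laboratory model.

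**Inputs**

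- 322 randomized 1:1, so 161 per arm, or about 145 after 10% dropout (SAP 4.2 and 4.3).
- Model terms: treatment only (SAP 10.3.2.1).
- Assumption: equal SD at baseline and follow-up, set to 1, with correlation rho. The documents give no rho, so a range is shown. With equal SDs the true baseline slope equals rho.

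**Precision.** Per-subject variance is 2(1 - rho) for the change score and 1 - rho^2 for ANCOVA. The ratio of ANOVA SE to ANCOVA SE is therefore sqrt(2/(1 + rho)), whatever the sample size.

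| rho | Variance saved by ANCOVA | ANOVA SE larger by | Power with ANCOVA for an effect with 80% under ANOVA |
|---|---|---|---|
| 0.3 | 35% | 24% | 93.5% |
| 0.5 | 25% | 15% | 90% |
| 0.7 | 15% | 8% | 86% |
| 0.8 | 10% | 5% | 84% |
| 0.9 | 5% | 3% | 82% |
| 0.95 | 2.5% | 1% | 81% |

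**Shift from a realised imbalance.** For a baseline difference D (active minus placebo), the change-score difference moves by -(1 - rho) x D. At rho 0.6, 161 per arm and D = 0.2 SD:

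- SE of a baseline difference = sqrt(2/161) = 0.111 SD, so 0.2 SD is about 1.8 SE.
- Size of shift = 0.4 x 0.2 = 0.08 SD.
- ANOVA SE = sqrt(2 x 0.4) x 0.1115 = 0.0997 SD, and 0.08/0.0997 = 0.8.

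**Type I error at about 145 per arm**

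| rho | Given no imbalance | Given a 1.96-SE imbalance |
|---|---|---|
| 0.5 | 2.4% | 12.9% |
| 0.7 | 3.4% | 9.8% |
| 0.9 | 4.4% | 6.6% |

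Averaged over randomizations the rate is 5%.

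**Simulation check.** 4,000 trials were simulated at each rho, with 145 per arm:

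| rho | Slope of ANOVA estimate on imbalance | Empirical SE, ANOVA / ANCOVA | Type I error, ANOVA / ANCOVA |
|---|---|---|---|
| 0.5 | -0.50 | 0.118 / 0.103 | 4.9% / 5.0% |
| 0.7 | -0.31 | 0.091 / 0.084 | 4.8% / 4.6% |
| 0.9 | -0.10 | 0.052 / 0.051 | 5.0% / 4.8% |

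The ANCOVA slope on imbalance was about zero throughout.

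**How often an imbalance arises.** SAP Table 12 lists 11 hematology and 21 chemistry analytes (leaving out the reflex-only INR). At the 5% level, 32 x 0.05 = 1.6 nominally significant baseline differences are expected by chance. Each one carries through the four post-baseline windows of SAP Table 2.

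These formulas are for absolute change. In percent change the baseline is also the denominator, so dependence on baseline is again an issue, but the table does not size it.

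**The case against.** The strongest reply is that nothing here is invalid. In a randomized trial an ANOVA on change is unbiased and holds its 5% level, and the simulation agrees. A reader might infer from the missing covariate that the test is biased or its error rate inflated. The documents do not support that: the shift exists only conditional on an imbalance that has occurred. Nor does the analysis disregard baseline altogether. Every value has its baseline subtracted, and baseline means are shown by arm. What is missing is an estimated slope.

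A reader might also infer that every continuous efficacy analysis in the SAP is adjusted. That is not so: the long-term analyses (SAP 9.1.1 and 9.3) are plain descriptive summaries. The contrast holds for Period 1 inference only, which has a confirmatory role that laboratory data lack.

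Further, no decision depends on these p-values. They sit outside the testing sequence of SAP 9.2.5, and most of the safety concerns are also covered by shift tables, Grade 3 or 4 counts, liver thresholds and summaries of events of special interest. The correlation is unknown, and for stable analytes the gain is small. A 0.2 SD imbalance is not typical: at about 1.8 SE it would occur in roughly 7% of comparisons. One linear slope may also fit a skewed analyte poorly.

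All of this stands, and it lowers the severity. It does not show the treatment-only model to be as good. The descriptive wording in the synopsis could equally be met by dropping the p-values, but the reported mean differences would still move with baseline imbalance.

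**Conclusion.** The point holds as one of precision and of conditional interpretation. The planned test is valid on average but less efficient than ANCOVA whenever the baseline slope differs from 1, and its estimate shifts by -(1 - rho) times any chance imbalance. The loss is modest for stable analytes (SE 1% to 5% larger for rho 0.95 to 0.8) and more noticeable for variable ones (8% to 24% for rho 0.7 to 0.3). These sizes rest on equal SDs, a linear baseline relation and a correlation that the documents do not supply. Severity is low: the ranked endpoints, the sample size and the confirmatory conclusions are untouched.

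**What to change.** In SAP 10.3.2.1, replace the ANOVA at each window by an ANCOVA with treatment, the baseline value of that parameter and the stratification factor country, for change and percent change alike. Use a log scale for markedly skewed analytes such as CPK. Report LS-mean differences with 95% CIs, and label the p-values nominal, because the protocol synopsis planned a descriptive analysis and these tests lie outside the multiplicity scheme.

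The cost is two covariates in the model, a skewness check per analyte and a short change of wording. No new data are needed, and no subject is lost, because anyone without a baseline value has no change score either. The precision figures above credit the baseline term only. Country is included because randomization is stratified by it, and to match the Period 1 efficacy models.

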10.3.2.2 Assessment of Shift from Baseline in Clinical Laboratory Variables

The baseline and post-baseline laboratory observations will be categorized as Grade 1, Grade 2, Grade 3, and Grade 4 according to OMERACT criteria (Rheumatology Common Toxicity Criteria v.2.0). For creatine phosphokinase and creatinine NCI CTC criteria will be used.

For each laboratory variable, shift tables will be generated that cross tabulate the subjects as deemed appropriate by "as treated" treatment group:

- Category of the baseline value versus category of the final value.
- Category of the baseline value versus maximum category.
- Category of the baseline value versus minimum category.

Note that the minimum/maximum category is used, rather than the category of the minimum/maximum value. The two may be different due to variation in the reference range.

No statistical tests will be performed for this analysis.

10.3.2.3 Assessment of Potentially Clinically Significant Laboratory Variables

The criteria for potentially clinically significant laboratory values will be determined by OMERACT criteria of Grade 3 or 4. For creatine phosphokinase and creatinine, NCI CTC criteria will be used.

The number and percentage of subjects meeting the criteria for potentially clinically significant laboratory values will be summarized by "as treated" treatment group. Only subjects with worsening in grade compared to baseline grade will be captured.

10.3.2.4 Assessment of Liver Elevations

According to FDA's Guidance for Industry "Drug-Induced Liver Injury: Premarketing clinical evaluation (July 2009), when aminotransferase (AT) abnormalities indicating hepatocellular injury are accompanied by evidence of impaired hepatic function (bilirubin elevation $> 2 \times$ ULN), in the absence of evidence of biliary obstruction (i.e., significant elevation of ALP) or some other explanation of the injury (e.g., viral hepatitis, alcohol hepatitis), the combined finding (i.e., Hy's Law cases) represents a signal of a potential for the drug to cause severe DILI.

For the purpose of assessing for potential Hy's law cases, the frequencies and percentages of subjects with post baseline liver specific function test values that meet the following criteria of potential clinical interest will be summarized by "as treated" treatment group:

- ALT $\geq 3 \times$ ULN
- ALT $\geq 5 \times$ ULN
- ALT $\geq 10 \times$ ULN
- ALT $\geq 20 \times$ ULN
- AST $\geq 3 \times$ ULN
- AST $\geq 5 \times$ ULN

- AST $\geq 10 \times$ ULN
- AST $\geq 20 \times$ ULN
- TBL $\geq 2 \times$ ULN
- Alkaline phosphatase $\geq 1.5 \times$ ULN
- ALT and/or AST $\geq 3 \times$ ULN and concurrent TBL $\geq 1.5 \times$ ULN
- ALT and/or AST $\geq 3 \times$ ULN and concurrent TBL $\geq 2 \times$ ULN

10.3.3 Analysis of Long-Term Laboratory Data

10.3.3.1 Assessment of Mean Change from Baseline and Percent Change from Baseline in Clinical Laboratory Variables

Analyses of mean change from baseline in continuous hematology, chemistry, and urinalysis variables which are measured longitudinally will be performed by visits and by "as treated" treatment group sequences as described in Section 10.1. For each change from baseline analysis, the following summary statistics will be presented for each treatment group: sample size, baseline mean, visit mean, and the mean, standard deviation, and median of the changes from baseline.

In addition, similar analyses will be performed for percentage change from baseline in hemoglobin, LDL-C, HDL-C, triglycerides, total cholesterol (TC), TC/HDL and LDL/HDL.

10.3.3.2 Assessment of Potentially Clinically Significant Laboratory Values

Long-term laboratory data will be summarized based on the number and percentage of subjects meeting the criteria for potentially clinically significant laboratory values for upadacitinib 15 mg QD group.

In the evaluation of potentially clinically significant laboratory values, the baseline value will be determined by the last non-missing measurement recorded on or before the date of the first dose of upadacitinib 15 mg QD (which may be different than the first dose of

study drug in the study). For example, for a subject who started on placebo and switched to upadacitinib 15 mg QD, lab values under upadacitinib 15 mg QD exposure would be evaluated against the baseline value defined as the last non-missing measurement recorded on or before the date of the first dose of upadacitinib 15 mg QD.

A listing of all subjects with any laboratory determination meeting OMERACT criteria of Grade 3 or 4 will be provided. For creatine phosphokinase and creatinine, NCI CTC criteria will be used. Only subjects with worsening in grade compared to baseline grade will be captured. For each of these subjects, the whole course of the respective parameter will be listed.

10.3.3.3 Assessment of Liver Elevations

The frequencies and percentages of subjects with post baseline liver-specific function test values that meet the following criteria of potential clinical interest will be summarized for upadacitinib 15 mg QD group, the categories are similarly described as in Section 10.3.2.4.

A listing of potentially clinically significant liver elevations based on criteria specified above will be provided. For each of these subjects, the whole course of the respective parameter will be listed.

10.4 Analysis of Vital Signs

10.4.1 Variables and Criteria Defining Abnormality

Vital sign variables include sitting systolic blood pressure, sitting diastolic blood pressure, pulse rate, respiratory rate, body temperature, and weight. The criteria for potentially clinically significant vital sign findings are presented in [Table 13](#).

Table 13. Criteria for Potentially Clinically Significant Vital Sign Findings

Vital Sign	Category	Criteria for Potential Clinically Significant Vital Signs
Systolic blood pressure	Low	Value \leq 90 mmHg and decrease \geq 20 mmHg from Baseline
	High	Value \geq 160 mmHg and increase \geq 20 mmHg from Baseline
Diastolic blood pressure	Low	Value \leq 50 mmHg and decrease \geq 15 mmHg from Baseline
	High	Value \geq 105 mmHg and increase \geq 15 mmHg from Baseline
Pulse	Low	Value \leq 50 bpm and decrease \geq 15 bpm from Baseline
	High	Value \geq 120 bpm and increase \geq 15 bpm from Baseline
Respiratory Rate	Low	< 10 rpm
	High	> 24 rpm
Body temperature	High	$> 39.0^{\circ}\text{C}$ (102.3°F)
Weight	High	$> 7\%$ increase from baseline
	Low	$> 7\%$ decrease from baseline

10.4.2 Analysis of Vital Sign for Period 1

Analyses of mean change from baseline in continuous vital sign variables which are measured longitudinally will be performed by visits and by the "as treated" treatment groups of upadacitinib 15 mg QD and placebo. For each change from baseline analysis, the following summary statistics will be presented for each treatment group: sample size, baseline mean, visit mean, and the mean, standard deviation, and median of the changes from baseline. The number and percentage of subjects meeting the criteria for potentially clinically significant vital sign values will be summarized by "as treated" treatment group.

10.4.3 Analysis of Long-Term Vital Sign

Analyses of mean change from baseline in continuous vital signs variables which are measured longitudinally will be performed by visits and by "as treated" treatment group sequences as described in Section 10.1. For each change from baseline analysis, the following summary statistics will be presented for each treatment group sequence: sample size, baseline mean, visit mean, and the mean, standard deviation, and median of the changes from baseline.

Long-Term Vital Sign will also be summarized based on the number and percentage of subjects meeting the criteria for potentially clinically significant vital sign values for upadacitinib 15 mg QD group. Similar baseline definition as described in Section 10.3.3.2 will be applied.

A listing of all subjects with any vital sign values meeting the criteria for potentially clinically significant vital signs will be provided. For each of these subjects, the whole course of the respective parameter will be listed.

